7.3 DATA AND SAFETY MONITORING PLAN

7.3.1 Principal Investigator/Research Team

The clinical research team will meet on a regular basis when patients are being actively enrolled on the trial to discuss each patient.

Any safety concerns, new information that might affect either the ethical and or scientific conduct of the trial, or protocol deviations will be immediately reported to the IRB via iRIS.

The principal investigator will personally conduct or supervise the investigation and provide appropriate delegation of responsibilities to other members of the research staff.

8 STATISTICAL CONSIDERATIONS

The primary objective of this study is to determine the ability of a set of markers to distinguish between benign and malignant adrenocortical neoplasms.

Patients with adrenal neoplasms greater than 2 cm will be enrolled onto the trial and a set of novel diagnostic and prognostic molecular markers will be evaluated. It is anticipated that approximately 10% of patients enrolled will have a malignant mass and 90% will be benign. Based upon pilot data, it is expected that the classification accuracy of the proposed methods will be 90% or better, but this study is intended to determine if this is correct and to improve the precision of the estimate of these results.

Assuming that 10% of patients have a malignant mass, it would be desirable to estimate the fraction of these correctly identified as being malignant, with a confidence interval width of +/-10% or less. Enrolling thirty five (35) patients who are ultimately determined to have malignant masses would permit an associated two-sided 95% confidence interval around 90% to have a width of +/-9.9%. It would also be desirable to estimate the fraction correctly identified as being benign. Enrolling 200 patients who are ultimately determined to have benign masses would permit an associated two-sided 95% confidence interval around 90% to have a width of +/-4.2%. Greater numbers of patients and a higher probability of correct classification will result in greater precision of the estimated classification probability.

Because the estimate is likely to be much less precise for identifying the malignant cases than for identifying those that are benign, it is important to enroll sufficient patients to ensure that at least 35 malignant cases are evaluated. Thus, if 10% is a reasonable estimate of the proportion of all patients expected to have malignant masses, it would be

desirable to enroll 350-500 total patients in order to have a reasonably high probability of obtaining at least 35 with malignant masses.

Classification will be done using standard logistic regression models and ROC curves as appropriate. The sensitivity and specificity will be reported along with 95% two-sided confidence intervals, and an AUC relative to the ROC curve will be determined. It is assumed that 50 patients per year may enroll onto this study. Thus, an accrual period of 10 years is anticipated in order to enroll up to 500 subjects.

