Eligibility:

- An individual with an adrenal neoplasm greater than 2 cm in size
- Age \geq 18 years
- Adults must be able to understand and sign the informed consent document

Design:

- Prospective observational study.
- Demographic, clinical, laboratory and pathologic data will be collected for each patient participant. Data will be securely stored in a computerized database.
- Patients will have biochemical testing to determine if their adrenal neoplasm is functioning or nonfunctioning.
- After their initial on-study evaluation, patients who are found to have a nonfunctioning adrenal tumor with a low risk of malignancy will be re-screened every year for 5 years with non-invasive imaging studies.

Abbreviated Title: Adrenal Neoplasm

Version Date: 06/05/2017

- Treatment of patients with an adrenal neoplasm will be performed based on standard clinical practice.
- Projected accrual will be 50 patients per year for a total of 10 years. Thus, we anticipate accruing 500 patients on this protocol.

TABLE OF CONTENTS

Précis.....	3
Table of Contents.....	5
1 Introduction	7
1.1 Study Objectives	7
1.2 Background and Rationale	7
2 Eligibility Assessment and Enrollment	8
2.1 Inclusion Criteria.....	8
2.2 Exclusion criteria.....	9
2.3 Registration procedures.....	9
3 Study Implementation.....	9
3.1 On Study Evaluation	10
3.2 CT guided fine needle aspiration biopsy of adrenal neoplasm	10
3.3 Surgical Intervention	10
3.4 Follow-up Examinations	11
3.5 Off Study Criteria.....	12
4 Concomitant medications/measures	12
5 BIOSPECIMEN COLLECTION	13
5.1 CORRELATIVE STUDIES FOR RESEARCH/PHARMACOKINETIC STUDIES	13
5.2 SAMPLE STORAGE, TRACKING AND DISPOSITION.....	14
6 Data Collection and Evaluation.....	14
6.1 Data Collection.....	14
6.2 Data Sharing Plans	15
6.3 Toxicity Criteria	15
7 SAFETY Reporting REQUIREMENTS/DATA AND SAFETY MONITORING PLAN	15
7.1 DEFINITIONS.....	15
7.2 NCI-IRB AND Clinical Director Reporting	17
7.3 Data and Safety Monitoring Plan	18
8 Statistical Considerations	18
9 Human Subjects Protections.....	19
9.1 Rationale for subject selection	19

9.2	Participation of Children	19
9.3	Participation of Subjects unable to give consent.....	19
9.4	Evaluation of Benefits and Risks/Discomforts	19
9.5	Consent Process and Documents.....	20
10	References.....	22
11	APPENDICES	25
11.1	Appendix A.....	25
11.2	Appendix B.....	28
11.3	Appendix C.....	29

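### The +/-9.9% precision at 35 malignant cases is a Wald half-width that understates the lower arm (13 to 15 points by better methods), and the plan names no interval method.

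*Combined protocol and SAP*

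**What the plan says.** Section 8 wants the fraction of malignant masses correctly identified to be estimated with a "confidence interval width of +/-10% or less". It plans around 90% because "it is expected that the classification accuracy of the proposed methods will be 90% or better". It then gives the precision for 35 malignant cases, a number which "would permit an associated two-sided 95% confidence interval around 90% to have a width of +/-9.9" per cent. The companion figure for 200 benign cases is +/-4.2%.

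The malignant figure leads to the enrolment requirement: "it is important to enroll sufficient patients to ensure that at least 35 malignant cases are evaluated". Section 8 takes 10% of patients to be malignant and arrives at 350 to 500 patients. The Précis (Design) says "we anticipate accruing 500 patients on this protocol".

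For the analysis, Section 8 says: "The sensitivity and specificity will be reported along with 95% two-sided confidence intervals". No method of calculating a binomial interval is named there or elsewhere in the document, for planning or for analysis.

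**The concern.** A proportion near 90% from 35 cases rests on very few failures. There the sampling distribution is skewed and a symmetric interval describes it badly. The side it describes too favourably is the lower one, which for sensitivity shows how many malignant tumours the markers might miss. A reader who takes +/-9.9 points at face value will think that side is tighter than it is, and the 35-case minimum is justified by that number.

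Because no method is named, the promised intervals could also be calculated in several ways that give visibly different lower limits at this sample size. Naming the method now removes a choice that could otherwise be made after the data are seen.

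**Working it through.** **Inputs, all from Section 8:** 35 malignant cases, 200 benign cases, expected proportion 0.90, two-sided 95% (z = 1.96), aim +/-10 points, malignant fraction 10%, up to 500 patients.

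**Step 1. Reproduce the plan's figures.** Wald half-width = z x sqrt(p(1-p)/n).
- n = 35: 1.96 x sqrt(0.09/35) = 0.0994, limits 80.1% to 99.9%. The stated 9.9% reproduces.
- n = 200: 1.96 x sqrt(0.09/200) = 0.0416. The stated 4.2% reproduces.
- Adding a continuity correction of 1/(2 x 35) = 0.0143 gives 0.1137, which does not match. The plan therefore used plain Wald.

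**Step 2. How well Wald works here.** Expected misclassified malignant cases: 35 x 0.10 = 3.5. With a true 90%, the Wald interval lies wholly above 90% when 34 or 35 of 35 are correct (binomial probability 12.24%). It lies wholly below when 26 or fewer are correct (0.63%). Coverage is 100 - 12.24 - 0.63 = 87.1%, and nearly all the failures are on the optimistic side. At the same point Wilson covers 92.0%, Jeffreys 95.5% and Clopper-Pearson 98.0%. Coverage moves with p, so a single point should not carry the argument. For true values from 0.80 to 0.95 in steps of 0.01, Wald covers 83.2% to 94.1%, below nominal throughout.

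**Step 3. Other intervals at the plan's inputs.** 90% of 35 is x = 31.5, which is not an attainable count, so these limits are interpolated.
- Wilson: centre (p + z²/2n)/(1 + z²/n) = (0.9 + 0.0549)/1.1098 = 0.8604. Half-width (z/(1 + z²/n)) x sqrt(p(1-p)/n + z²/4n²) = (1.96/1.1098) x sqrt(0.002571 + 0.000784) = 0.1023.
- Clopper-Pearson: 2.5% quantile of Beta(x, n-x+1) and 97.5% quantile of Beta(x+1, n-x), that is Beta(31.5, 4.5) and Beta(32.5, 3.5).
- Jeffreys: 2.5% and 97.5% quantiles of Beta(x+0.5, n-x+0.5), that is Beta(32, 4).

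| Method, 31.5/35 | 95% limits | Half of total width (points) | Lower arm (points) |
|---|---|---|---|
| Wald | 80.1-99.9% | 9.9 | 9.9 |
| Wilson | 75.8-96.3% | 10.2 | 14.2 |
| Clopper-Pearson | 75.1-97.5% | 11.2 | 14.9 |
| Jeffreys | 76.9-96.8% | 9.9 | 13.1 |

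**Step 4. Attainable counts.** Limits, with half of total width in brackets:

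| Method | 31/35 (88.6%) | 32/35 (91.4%) |
|---|---|---|
| Wald | 78.0-99.1% (10.5) | 82.2-100.7% (9.3) |
| Wilson | 74.0-95.5% (10.7) | 77.6-97.0% (9.7) |
| Clopper-Pearson | 73.3-96.8% (11.8) | 76.9-98.2% (10.6) |
| Jeffreys | 75.1-96.0% (10.5) | 78.9-97.5% (9.3) |

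Except under Clopper-Pearson, one patient decides whether the half-width is under 10. At both counts the Wald lower limit is about 3 to 5 points above the others.

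**Step 5. The number expected at full accrual.** 0.10 x 500 = 50 malignant cases. At 45/50: Wilson 78.6-95.7% (8.5), Clopper-Pearson 78.2-96.7% (9.2), Jeffreys 79.5-96.1% (8.3). All are within +/-10.

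**Step 6. The benign figure.** At 180/200, half the total width is 4.2 by Wilson and 4.4 by Clopper-Pearson. The stated +/-4.2% needs no correction.

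**The case against.** The strongest defence is that the plan sets an aim for width only, and describes it as desirable. It names no minimum acceptable sensitivity and no decision rule. On that criterion the shift is small: half the total width goes from 9.9 to 9.9 (Jeffreys), 10.2 (Wilson) or 11.2 (Clopper-Pearson). Moreover, 35 is a floor. With 500 patients about 50 malignant cases are expected, and the binomial chance of at least 35 is 99.2% if the 10% holds. At 50 cases every method meets the aim. Section 8 also notes that more patients, or better classification, would improve precision. All of this stands, and it is why no design decision turns on the point.

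It does not remove the point. The precision claim is made at 35 cases, in a symmetric form that hides a lower arm of 13 to 15 points. At the lower end of the enrolment range, 350 patients, 35 is itself the expected number (0.10 x 350), with only a 53% chance of reaching it.

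A reader might infer three stronger things, and the documents support none of them:
- **The plan promises a lower limit of 80%.** That figure follows only from subtracting 9.9 from 90; the plan never states it. The larger samples needed to reach 80% by other methods (55 to 65 cases) therefore answer a question the plan did not ask.
- **The 9.9% is an arithmetic error.** It is correct for the Wald formula.
- **The analysis will use Wald.** The plan does not say so. The method is simply unspecified.

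**Conclusion.** The point holds as a minor one about stated precision and an unnamed method. At 35 malignant cases and 90% correct, a better-behaved interval runs from about 75-77% to about 96-98%. Its lower arm is 13 to 15 points, where the plan shows 9.9. Half the total width is 9.9 to 11.2 points, so it cannot be said outright that the +/-10% aim fails at 35 cases; that depends on the method chosen.

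This rests on the plan's own 90%, on an interpolated 31.5 of 35, and on treating the cases as independent with a known final diagnosis. At the attainable counts on either side the lower limits run from 73.3% to 78.9% under the three non-Wald methods, so the conclusion does not depend on the interpolation.

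**What to change.** In Section 8, name one non-Wald method, for example Wilson or Clopper-Pearson, for the two-sided 95% intervals for sensitivity and specificity, and use it for both planning and analysis. Replace the +/-9.9% with the asymmetric interval under that method at 35 and at about 50 cases:

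- *If Wilson:* 35 malignant cases with 90% correctly identified give about 76% to 96%; the roughly 50 cases expected with 500 patients give about 79% to 96%.
- *If Clopper-Pearson:* 35 cases give about 75% to 98%; 50 cases give about 78% to 97%.

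The aim of +/-10% or less must then be reconciled, because under either method 35 cases just miss it. Tie the aim to the roughly 50 expected cases (half-width 8.5 points by Wilson, 9.2 by Clopper-Pearson). State that the 35-case minimum gives 10.2 or 11.2 respectively. A symmetric range spanning both methods should not stand in for the limits, since it would hide the lower arm again.

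The 35-case minimum and the 500-patient accrual stay as they are. The cost is a few sentences and a slightly less favourable stated precision at 35 cases. Each method also has its own trade-off at 35 cases and a true 90%: Wilson covers a little under nominal (92.0%), and Clopper-Pearson is conservative (98.0%) and so wider.

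### At the plan's own 10% malignant rate, the lower end of the 350-500 enrolment range gives a 53% chance of at least 35 malignant cases, not a reasonably high one; the planned 500 gives 99%

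*Combined protocol and SAP*

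**What the plan says.** Section 8 plans the study around the precision of the estimated fraction of malignant masses classified correctly. It aims for a two-sided 95% confidence interval of plus or minus 10 points or less, and reports that 35 malignant cases give 9.9 points around 90%. For benign masses, 200 cases give 4.2 points. The assumed mix is that "approximately 10% of patients enrolled will have a malignant mass", and "it is expected that the classification accuracy of the proposed methods will be 90% or better".

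Because the malignant group is the smaller one, the section adds that "it is important to enroll sufficient patients to ensure that at least 35 malignant cases are evaluated". The next sentence turns this into a total: if 10% is reasonable, it would be "desirable to enroll 350-500 total patients in order to have a reasonably high probability of obtaining at least 35 with malignant masses". No numerical probability is given.

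On the planned size, section 8 ends by saying that "an accrual period of 10 years is anticipated in order to enroll up to 500 subjects", at 50 patients per year. The Précis (Design) says "we anticipate accruing 500 patients on this protocol".

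**The concern.** The lower end of the range equals 35/0.10. Enrolling the number at which the expected count just equals the requirement gives roughly an even chance of reaching it. That fits neither a reasonably high probability nor the aim, one sentence earlier, of ensuring 35 cases.

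What is at stake is the justification for any total below 500. The documents set no minimum enrolment and no rule that ties the end of accrual to the malignant count. Section 3.5 lists the investigator's decision to close the study without a size condition. At 50 patients per year, 350 is reached after 7 of the 10 years. A team that stopped there could cite this sentence for an assurance that 350 does not give, and the affected estimate is sensitivity, which section 8 itself expects to be the less precise one.

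**Working it through.** **Inputs, all from section 8:** malignant rate p = 0.10; required malignant cases 35; enrolment range 350 to 500; sensitivity 90% for planning; two-sided 95% interval; target half-width 10 points.

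**1. The plan's printed figures.** Normal-approximation half-width = 1.96 × √(s(1−s)/m), with s = 0.90:

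- m = 35: 1.96 × √(0.09/35) = 0.0994, or 9.9 points, as printed.
- m = 200: 1.96 × √(0.09/200) = 0.0416, or 4.2 points, as printed.
- A half-width of 10 points needs m = 1.96² × 0.09/0.01 = 34.6, so 35 cases.

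The requirement of 35 is right for the stated target.

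**2. Origin of the lower end.** 35/0.10 = 350, so the expected malignant count at 350 patients is exactly 35.

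**3. Probability of at least 35 malignant cases.** X ~ Binomial(N, 0.10), exact upper tail P(X ≥ 35):

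| N | Years at 50/year | Expected count | P(X ≥ 35) |
|---|---|---|---|
| 350 | 7 | 35 | 0.526 |
| 400 | 8 | 40 | 0.820 |
| 450 | 9 | 45 | 0.955 |
| 500 | 10 | 50 | 0.992 |

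As a check, the normal approximation with continuity correction gives 0.535 at 350 and 0.990 at 500. The smallest N reaching 80%, 90% and 95% are 396 (0.802), 424 (0.902) and 447 (0.950).

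**4. What a shortfall costs in precision.** At s = 0.90, 34 cases give 1.96 × √(0.09/34) = 10.1 points. With 28 cases, the 10th percentile of the count at N = 350, the half-width is 11.1 points.

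**5. If sensitivity is above 90%.** Fewer cases then meet the 10-point target:

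| Sensitivity | Cases needed | P(reached at N = 350) | P(missed) |
|---|---|---|---|
| 90% | 35 | 0.526 | 47% |
| 91% | 32 | 0.729 | 27% |
| 92% | 29 | 0.879 | 12% |
| 93% | 26 | 0.959 | 4% |

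**6. If some malignant cases have no usable marker result.** The documents give no loss rate, so the shares here are assumptions. With 90% or 80% evaluable, the effective rate is 0.09 or 0.08, and P(X ≥ 35) becomes:

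| N | 90% evaluable | 80% evaluable |
|---|---|---|
| 350 | 0.282 | 0.103 |
| 400 | 0.595 | 0.315 |
| 450 | 0.839 | 0.594 |
| 500 | 0.954 | 0.817 |

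**The case against.** The best defence has four parts.

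- **No printed number is wrong.** The sentence uses an undefined phrase, hedged twice: 10% is conditional and the range is only desirable. It can be read as 350 for the expected count, with the rest of the range as a cushion. The first part is true. But the sentence offers the whole range as the enrolment that delivers the probability, straight after an aim to ensure the count, and no ordinary reading of the phrase covers 53%.
- **The operative size is 500, and nothing makes 350 a minimum or a stopping point.** This stands, and it limits the point to one end of one sentence. It does not make the sentence correct, because the 500 is worded as a ceiling.
- **The practical loss is small.** This also stands: the half-width is 10.1 points at 34 cases, and the miss rate at 350 falls quickly if sensitivity exceeds 90%. Nor is 35 a strict pass line, since the reported interval depends on the observed sensitivity. With 35 cases, 31 correct gives 1.96 × √((31/35)(4/35)/35) = 10.5 points, and 32 correct gives 9.3. The case counts above are planning values.
- **The evaluable shares have no anchor in the documents.** Agreed. They are shown only as a range, and the conclusion does not depend on them.

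**Conclusion.** The concern holds. At the plan's 10% rate with every malignant case evaluable, 350 patients give a 53% chance of at least 35 malignant cases, a 47% chance of falling short. The assurance rises to 99% at 500.

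The result rests on a fixed 10% rate, independent patients and the plan's own requirement of 35. Any loss of evaluable cases lowers the probability. A sensitivity above 90% makes a shortfall in the count less important for the precision target.

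This is a correction to a stated assurance that should be made. It is not a flaw in the planned accrual of 500, which meets the aim under the plan's assumptions, and the printed half-widths need no change.

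**What to change.** Replace the sentence in section 8 with wording such as: *At a 10% malignant rate, the probability of at least 35 malignant cases is 53% with 350 patients, 82% with 400, 95% with 450 and 99% with 500, if all are evaluable; the planned accrual is therefore 500.* Drop the claim that 350 gives a reasonably high probability.

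If the sponsor wants to keep a lower end, it should choose one from these figures and state the assurance it accepts: 396 patients for 80%, 424 for 90%, 447 for 95%. Any allowance for malignant cases without a usable marker result should be labelled as an assumption; at 500 patients, 90% or 80% evaluable gives 95% or 82%.

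The cost is one sentence, with no change to the design, the planned 500 or the 10-year accrual. The downside is that the lower end looks less favourable, and stopping well short of 500 becomes harder to justify.

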Postoperative histopathologic examination to distinguish between malignant and benign primary adrenal tumors is also difficult and problematic. For adrenocortical neoplasms, the Weiss histologic criterion is most commonly used, but is imprecise [21-23]. This means even patients with histologically diagnosed adrenocortical adenoma require continued follow-up because some will develop metastatic disease [11].

In summary, although adrenocortical carcinomas tend to be larger than benign tumors, tumor size, even when combined with imaging features, is not accurate enough to use for making management decisions for most tumors that are less than 6 cm. Furthermore, imaging studies such as MRI and CT scans underestimate adrenal tumor size by 16% to 47%, and are less accurate in smaller tumors [24-26]. Therefore, there is a significant need for biomarkers that can distinguish benign from malignant adrenal tumors for determining the need for adrenalectomy, for selecting the appropriate surgical approach, and for determining the appropriate follow up.

We and others have used genome profiling approaches (mRNA, microRNA) to identify diagnostic and prognostic markers of malignant adrenocortical tumors [27-31]. In our studies, we have identified several novel diagnostic markers with excellent accuracy for distinguishing between benign and primary malignant adrenocortical tumors ([Appendix A](#)). While these markers could be used in post-surgical resection samples in equivocal cases, the most helpful clinical application of these markers would be preoperatively in clinical fine needle aspiration biopsy samples. Therefore, we propose to test the feasibility and accuracy of using this panel of markers in fine needle aspiration samples of patients with adrenal neoplasm with the exception of pheochromocytoma that are greater than 2 cm. For cytologic examination, fine needle aspiration biopsy has a 67%-100% adequacy rate [32, 33]. Our previous studies in thyroid fine needle aspiration biopsy samples indicate an adequate yield of nucleic acid for multigene expression analysis [34]. Moreover, we are able to determine gene expression levels in as little as 10 adrenocortical carcinoma cells by quantitative RT PCR ([Appendix B](#)).

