5 BIOSPECIMEN COLLECTION

5.1 CORRELATIVE STUDIES FOR RESEARCH

5.1.1 Adrenal biopsy and surgical specimens

The adrenal fine needle aspiration will be performed at the NIH Clinical Center. Patients will undergo one biopsy. A portion of the FNA sample will be sent to the department of pathology, and the remainder to the Endocrine Oncology laboratory. The biopsy sample will be immediately placed in RNAlater®, transported on ice, and stored in -80°C until used for molecular analysis. For the surgical resection specimen, the samples will be immediately snap frozen in liquid nitrogen and stored in -80°C until molecular analysis.

Samples will be immediately transported to:

NCI Endocrine Oncology Laboratory
[name]
[name]
[name]
[contact]

[figure not shown]

Figure 1. Flow diagram of specimen collection and analysis.

The diagnostic accuracy of the candidate gene expression levels will be determined based on the histologic diagnosis and follow up time of over 5 years. We will also analyze the gene expression level relative to disease-free survival and overall survival in patients with adrenocortical carcinoma. All the candidate gene expression level thresholds/cutoffs will be normalized to an adrenocortical carcinoma cell line and universal RNA to account for interassay variability.

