11 APPENDICES

11.1 APPENDIX A

Molecular markers of adrenocortical carcinoma

Table 1.

Messenger RNA candidate diagnostic markers	Gene Symbol	P value* (1)	P value* (2)	AUC (1)	AUC (2)
	PRLR	0.011	0.01	0.74	0.75
	HSD3B2	< 0.01	0.01	0.77	0.75
	PRG-3	< 0.01	0.01	0.76	0.75
	LGR5	0.01	0.008	0.74	0.76
	FREM2	0.006	< 0.01	0.70	0.80
	ALDH1A1	< 0.01	< 0.01	0.76	0.81
	CCNB2	< 0.01	< 0.01	0.86	0.84
	SLC16A9	< 0.01	< 0.01	0.80	0.87
	RARRES2	< 0.01	< 0.01	0.86	0.88
	HTR2B	< 0.01	< 0.01	0.87	0.88
	IL13RA2	< 0.01	< 0.01	0.90	0.91

Abbreviations: AUC, area under the receiver operating characteristic curve.

*P values were determined by Mann-Whitney test.

(1) = Analysis based on benign (54 adrenocortical adenoma, 20 adrenocortical hyperplasia, 4 normal adrenocortical tissue) and malignant (11 primary adrenocortical carcinomas) tissue samples.

(2) = Subset analysis of benign vs. malignant adrenocortical tumors excluding Conn's syndrome (n= 30) and normal (n= 4) adrenocortical tissue samples.

The combination of the highest AUC 5 genes did not show improvement in diagnostic accuracy when compared to the highest individual value (AUC: 0.913 for IL13RA2 vs. 0.907 all 5 genes in combination. Comparison of the 5 markers with the highest AUC to tumor size, one of the main current clinical criterions used to assess risk of malignancy, demonstrates that the candidate markers in combination are more accurate than tumor size (**Figure 1**).

[figure not shown]

Figure 1. Area under receiver operating characteristics curve (AUC) when the 5 biomarkers with the highest individual AUC values (IL13RA2, HTR2B, CCNB2, RARRES2, SLC16A9) were combined as compared to tumor size as a clinical parameter for the diagnosis of adrenocortical carcinoma (AUC: 0.79). An AUC of 1 represents the perfect diagnostic biomarker without any false-negative and false-positive results.

Table 2. MicroRNA Candidate Diagnostic Markers

microRNA[^]	p value	(Benign v. Malignant)	AUC
miR-665	0.0042		0.83
miR-483-5p*	<0.0001		0.94
miR-483-3p*	<0.0001		0.94
miR-23b	0.0376		0.78
miR-195*	0.014		0.77
miR-125b	0.0173		0.76

Abbreviations: AUC, area under the receiver operating characteristic curve.

P values were determined by Mann-Whitney test.

Analysis based on benign (54 adrenocortical adenoma) and malignant (11 primary adrenocortical carcinoma) tissue samples.

*Also identified as a prognostic marker in patients with adrenocortical carcinoma

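### Section 8 does not say where the classification rule comes from; if it is built and tested in the same patients, reported sensitivity is optimistic by roughly 0 to 7.6 points with one to five markers

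*Combined protocol and SAP*

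**What the plan says.** The analysis plan is two sentences in Section 8: "Classification will be done using standard logistic regression models and ROC curves as appropriate", followed by "The sensitivity and specificity will be reported along with 95% two-sided confidence intervals, and an AUC relative to the ROC curve will be determined".

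The same section expects accuracy of 90% or better from pilot data and adds that "this study is intended to determine if this is correct and to improve the precision of the estimate of these results". It makes sensitivity the driver of enrolment: "it is important to enroll sufficient patients to ensure that at least 35 malignant cases are evaluated". It gives 95% half-widths of 9.9 points for 35 malignant cases and 4.2 points for 200 benign cases, both around 90%.

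Elsewhere, Section 1.2 says "we propose to test the feasibility and accuracy of using this panel of markers in fine needle aspiration samples". Appendix A lists the candidates: 11 mRNA markers (Table 1) and 6 microRNAs (Table 2). Section 5.1.1 mentions cut-offs, but only to say how they are scaled: "All the candidate gene expression level thresholds/cutoffs will be normalized to an adrenocortical carcinoma cell line and universal RNA". Appendix A also reports a five-gene combination, and there "The combination of the highest AUC 5 genes did not show improvement in diagnostic accuracy when compared to the highest individual value" (0.907 against 0.913).

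**The concern.** The candidate pool is named, but the rule is not. The text supports two different studies. Checking whether pilot accuracy is correct, and normalising cut-offs, both suggest a rule carried forward from earlier work. Logistic regression and ROC curves, used as appropriate, suggest a rule fitted in this cohort.

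The difference matters because a rule tuned and scored on the same patients looks better than it is. Sensitivity is the exposed measure: it rests on few cases and it sets the sample size. In one plausible setting (five genes, Youden cut-off), a rule that detects 81% to 83% of cancers in new patients would be reported on average at 88% to 90%. It would then appear to confirm the pilot expectation. From the report alone, a reader could not tell whether this had happened.

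**Working it through.** **1. The plan's own figures.** The half-width is 1.96 × √(p(1−p)/n) with p = 0.90.

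- n = 35: 1.96 × √(0.09/35) = 0.099.
- n = 200: 1.96 × √(0.09/200) = 0.042.

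Both match Section 8. The formula treats each patient as an independent trial of a rule fixed before the data are seen.

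**2. Inputs for the in-cohort case.**

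- 35 malignant and 315 benign cases: 35 is the target in Section 8, and 315 follows from 10% malignancy in 350 patients.
- One marker at AUC 0.90 (IL13RA2, Table 1 column 1) or 0.94 (the miR-483 markers, Table 2).
- Five genes at AUC 0.84, 0.87, 0.88, 0.88 and 0.91 (Table 1 column 2), the set in Appendix A Figure 1: "when the 5 biomarkers with the highest individual AUC values (IL13RA2, HTR2B, CCNB2, RARRES2, SLC16A9) were combined".
- Assumptions not in the documents: binormal markers, and pairwise correlation 0.5 or 0.7 among the five genes.

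**3. Model.** A benign value is N(0,1) and a malignant value is N(δ,1), with δ = √2 × Φ⁻¹(AUC). For AUC 0.90, δ = 1.414 × 1.282 = 1.81. True sensitivity at 90% specificity is then Φ(1.81 − 1.28) = Φ(0.53) ≈ 0.70, in line with the simulated 0.699 below. Each replicate fits a logistic model, sets the cut-off, scores the same patients (apparent) and computes the fitted rule's true sensitivity from the model. Coverage is the share of 95% Wilson intervals around the apparent value that contain the true value. There were 2000 replicates per row, with Monte Carlo error of the bias 0.2 point or less.

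| Rule | Cut-off | Apparent | True | Bias (points) | Coverage |
|---|---|---|---|---|---|
| One marker, AUC 0.90 | 90% specificity | 0.701 | 0.699 | +0.2 | 95.0% |
| One marker, AUC 0.94 | 90% specificity | 0.819 | 0.818 | +0.1 | 94.8% |
| Five genes, correlation 0.5 | 90% specificity | 0.826 | 0.800 | +2.6 | 94.9% |
| Five genes, correlation 0.7 | 90% specificity | 0.772 | 0.745 | +2.7 | 94.3% |
| One marker, AUC 0.90 | Youden | 0.855 | 0.799 | +5.6 | 91.6% |
| One marker, AUC 0.94 | Youden | 0.897 | 0.847 | +5.0 | 93.2% |
| Five genes, correlation 0.5 | Youden | 0.900 | 0.830 | +7.0 | 85.8% |
| Five genes, correlation 0.7 | Youden | 0.882 | 0.807 | +7.5 | 85.4% |

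A repeat with separate code gave +7.6 points and 84% coverage for both five-gene Youden rows. The cut-off closest to the (0,1) corner falls between the two rules shown.

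**4. Selection in the data.** The one-marker rows hold only if the marker is named beforehand. Picking the best of the 17 candidates in the study data gives about +2.6 points at 90% specificity and +6.9 with Youden.

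**5. Other settings.**

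- With 50 malignant and 450 benign cases, and one or five pre-named markers, the bias is 0.0 to 1.8 points (90% specificity) and 3.9 to 5.7 (Youden).
- With one to five markers, specificity shifts by at most 0.7 point and AUC by at most 0.012.
- Larger models do worse. With 35 malignant cases, and a shared-signal model that caps the combined AUC at 0.92 (mRNA) or 0.95 (all 17), the bias is about 5 to 12 points for all 11 mRNA markers and 9 to 15 for all 17. The protocol does not say that such models will be fitted.
- A rule trained on the pilot numbers and applied unchanged to 35/315 has bias of 0.2 point or less and coverage of 95% to 96%.

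**The case against.** The strongest reply is that nothing here is a demonstrated error. Section 8 is a short statistics section, its wording does not exclude internal validation, and both its stated purpose and Section 5.1.1 fit a rule carried forward, for which the bias disappears. This stands, and it makes the concern conditional. The specimen and analysis flow diagram in Section 5.1.1 could not be read here, so the omission is claimed only for the readable text.

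A second reply is that the pilot saw no gain from combining five genes, so a single marker is likely and the harm is small. This stands only in part. It needs the marker to be named beforehand, which it is not, and under Youden even a pre-named marker carries about 5 points.

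Third, the sizes depend on an assumed model. The five-gene settings imply combined AUCs of 0.938 and 0.920, above the pilot's 0.907. However, the shared-signal model, capped at 0.92 for the mRNA markers, gave about 0 to 6 points for one marker and 2 to 8 for five, so the scale does not rest on one choice.

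A reader might infer that the plan commits to fitting and testing in the same patients, or that its markers are unspecified. The documents support neither: the first is left open, and Appendix A lists the candidates.

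**Conclusion.** The point holds as a conditional one. No readable text fixes the final panel, coefficients, cut-off or cut-off rule, or names a validation step, while the stated precision presumes a fixed rule. If the rule is derived in the study patients, sensitivity is overstated by about 0 to 6 points (one pre-named marker), 2.6 to 7 (best of 17 chosen in the data) or 2.6 to 7.6 (five markers), and by more with larger models. The upper end approaches the planned 9.9-point margin. Specificity and AUC are little affected with up to five markers.

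These sizes rest on binormal markers at the pilot AUCs, the assumed correlations and 35/315 cases. They depend on the number of markers and on selection as much as on the cut-off rule. It would go too far to say that the study's sensitivity will be biased by 8 points or that it cannot test the 90% expectation; with a locked rule it can do so without this bias. The gap should be closed before outcomes are seen, with moderate confidence in the exact sizes.

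**What to change.** Amend Section 8 to state where the rule comes from, in one of two ways. Neither is ranked first.

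**(a) Lock it.** Write down the panel, coefficients and cut-off before outcomes are seen, and evaluate them unchanged in all study patients. Under Section 5.1.1, FNA samples go into RNAlater and resected samples are snap frozen, while the pilot used tissue. Any rescaling between sample types should therefore be set without using outcomes.

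*Cost:* the pilot has only 11 carcinomas. Compared with a rule fitted in this cohort, the locked rule loses about 2 to 9 points of true sensitivity. For five genes at the 90%-specificity cut-off it also loses about 1.5 points of specificity if trained on 11/78. The loss is about 3 points if trained on 11/44 (0.860 against 0.894). The 44 is 78 less the 30 Conn's and 4 normal samples excluded from the column that supplies the five AUCs.

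**(b) Derive it here and correct for optimism.** Pre-name a small panel and one cut-off rule, for example a target specificity of 90%, which is Section 8's own planning value. Make bootstrap optimism-corrected sensitivity, specificity and AUC primary, repeating any selection, fitting and cut-off choice in every resample. Put a Wilson interval around the corrected sensitivity with n equal to the malignant cases, and report apparent figures as secondary.

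*Cost:* some analyst time and a small residual bias, up to roughly 2 to 3 points with Youden and under 1 point with fixed specificity. In simulation this interval covered 94% to 97% with one to five pre-named markers, and about 91% to 98% when selection was included (150 to 300 replicates).

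Neither option needs new patients or samples. Under both, Section 8 should note that 9.9 points applies only at 90% sensitivity: 1.96 × √(0.16/35) = 13.3 points at 80%, and 1.96 × √(0.1875/35) = 14.3 points at 75%.
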